International Multicenter Double-blind Placebo-Controlled Parallel-Group Randomized Clinical Trial of Efficacy and Safety of Ergoferon in the Treatment of Viral Intestinal Infections in Children

Phase IV

Sponsor OOO «NPF «MATERIA MEDICA HOLDING»

Protocol number MMH-ER-008

Version date: November 02, 2015

ClinicalTrials.gov Id: NCT03039699

Protocol Summary

This document represents the protocol summary for the study on human subjects. The study will be carried out in accordance with ICH GCP, National Standard of the Russian Federation GOST 52379-2005 "Good Clinical Practice", Helsinki Declaration of World Medical Association, relevant requirements of the regulatory authorities as well as the study procedures.

Title of Study

International multicenter double-blind placebo-controlled parallel-group randomized clinical trial of efficacy and safety of Ergoferon in the treatment of viral intestinal infections in children.

Phase: IV

Sponsor: OOO "NPF "Materia Medica Holding", Moscow, Russia

Protocol No. MMH-ER-008

Objective of the study

• To obtain additional data on the efficacy and safety of Ergoferon in the treatment of viral intestinal infections in inpatient children.

Endpoints

Primary endpoint

1. Average diarrhea duration¹.

Secondary endpoints

- 1. Percentage of patients without diarrhea following 48, 72, and 96 hours of treatment.
- 2. Percentage of patients with recovery² following 48, 72, and 96 hours of treatment.
- 3. Average illness duration (from the enrollment to the recovery).
- 4. Total CDS score at 24, 48, and 72 hours after treatment initiation.
- 5. Average vomiting duration (if any).
- 6. Percentage of patients with negative PCR tests on Days 3, 4, 6, and 10 of observation versus baseline (no RNA detection of rotaviruses/ noroviruses/ astroviruses/ adenoviruses in patients who had positive tests at baseline).
- 7. Percentage of patients with worsening of illness³ and/or hospital-acquired infection⁴.

CONFIDENTIAL Page 2 of 14

¹ Diarrhea duration is considered as the time between receiving the first dose of investigational medicine /placebo and the normal consistency of stool pattern (to the previous stool consistency before diarrhea), i.e.

¹⁾ time to the first loose stool which is followed by two normal consistency stools over 24 h (infants may have three episodes of loose stool over a 24-hour period), or 2) time to ≤3 episodes of stool occurring over 24 h, at least 2 of which are normal consistency stools, or

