⁶ The data of a patient whose PCR test indicates a bacterial etiology of acute intestinal infection will not be included in the analysis of treatment efficacy. For the sake of sufficiency of data for the efficacy analysis, it is statistically assumed that 50% of patients will test negative for viral etiology of acute intestinal infection.

pediatrician, and the examination results, including the CDS scores, will be recorded in source documents. The patient's parent/adopter will fill patient diary on a daily basis, recording the presence/absence of diarrhea signs, vomiting, and body temperature. The pediatrician will check correctness of diary filling. After discharge on day $10 \ (\pm 1)$ Visit 7 is scheduled (personal at the site/at home or distant/phone call) to interview the parents/adopters about the patient's health, presence of any complications, and use of medications (the investigator will fill out a questionnaire).

Collection of stool specimens and repeat PCR for Rotaviruses/Noroviruses/Astroviruses/Adenoviruses, Shigella spp., EIEC, Salmonella spp., and Campylobacter spp. will be performed on Days 3, 4, and 6 of inpatient observation and after discharge from the hospital (Day 10); collection of blood and urine specimens for safety tests will be carried out at baseline and before hospital discharge (day 6). The recording of the intake of study therapies and of concomitant medications as well as the assessment of compliance with and safety of the study therapies will be performed on Days 2-6 and 10.

Patients who recovered while in hospital and are discharged from the unit earlier than at 5 days will undergo the procedures of Visit 6, including the collection of biological specimens for PCR (efficacy evaluation) and biochemistry, blood test and urinalysis (safety assessment). The parents/adopters will be given the blister pack with the remaining study drug so that the patient can continue the treatment.

Inclusion and exclusion criteria

Inclusion criteria

- 1. Patients of either gender aged from 6 months to 6 years old hospitalized to infectious department.
- 2. Diarrhea (watery stool without visible abnormal foreign substances [transparent mucus is possible] ≥ 3 times a day).
- 3. Dehydration symptoms according to CDS scale ≥ 1 .
- 4. The first 48 hours from the onset of the first diarrhea episode.
- 5. Start of study treatment (Ergoferon/Placebo) within 12 hours after the start of the standard hospital therapy.

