Medical history	+						
Physical examination	+	+	+	+	+	+	
Body weight measurement	+					+	
Body length/height measurement	+						
Evaluation of dehydration symptoms using CDS	+	+	+	+	+	+	
Diary supply	+						
Checking the correctness of filling the diary		+	+	+	+	+	
Parent/adopter inquiry (personal/by phone) and filling questionnaire "Parent's/adopter's inquiry data"							+
Return of patient diary						+	
Concomitant therapy	+	+	+	+	+	+	+
Eligibility assessment	+						
Obtaining stool sample for PCR diagnosis	+		+	+		+	+*
Safety laboratory tests (hematology, serum chemistry,	+					+	

CONFIDENTIAL Page 9 of 14

urinalysis)							
Randomization and prescription of study drug	+						
Study drug supply							
, , , , , , , , , , , , , , , , , , ,	T .						
Basic medication supply	+	+	+	+	+		
Study drug accountability,						+ **	+ **
compliance assessment						Į.	!
Evaluation of treatment safety	+	+	+	+	+	+	+

^{*} All the subjects will receive sterile containers for stool storage and transportation on day 10. In case of a phone visit on day 10 stool samples will be delivered to the local laboratory by a courier.

Statistical Analyses.

Samples

Total set: all patients included in the study whose parents/adoptive parents signed the Informed Consent Form for the patient's participation in the study. All AEs including those occurred prior to the study therapy will be considered throughout the study for this sample.

Safety population: all patients who received at least one dose of the study drug. This sample will be used to *analyze the study treatment safety and tolerability*, since all the AEs identified after the study product administration will be recorded.

Full Analysis Set. This sample includes all enrolled and randomized patients, except for those who have experienced at least one of the following events:

- 1) non-compliance with inclusion / exclusion criteria;
- 2) the patient has not taken a single dose of the study drug;
- 3) lack of any data of the patient following randomization;
- 4) withdrawal of a patient due to early discharge (discharge of patient with persistent symptoms of acute intestinal infections on days 2-5 of hospitalization before the study treatment is completed at the parent's/adopter's request).

This sample is the most consistent with the "Intention-to-treat" principle, will be used for the *Intention-to-treat analysis (ITT analysis) of the the study therapy efficacy*.

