Per protocol set. This sample includes all patients who completed the therapy as per the study protocol without any missing visits or significant protocol deviations. This sample will be used for the *Per Protocol analysis (PP- analysis) of the the study therapy efficacy*.

Mean value in Placebo group for the relevant day will be used to fill lacking/missing data.

Data treatment and all statistical calculations under the protocol will be made using SAS-9.4 statistical software¹⁰.

CONFIDENTIAL Page 10 of 14

^{**} Return of the study product is made after 5-day treatment course (on Day 6). If the subject is discharged sooner than on day 6, the parent/adopter will be given a blister with the remaining product to complete outpatient therapy; in this case the product return and determination of compliance will be made on Day 10 ± 1 .

¹⁰ Holder of license: OOO "NPF "Materia Medica Holding", No. 70100045.

Evaluation of sample size

The sample size has been assessed on the basis of the following rules and assumptions:

- 1. Statistical provisions.
 - 1.1 the power of the statistical tests " $P = (1 \beta)$ " is assumed to be 80% (the probability of correct rejection of the null hypothesis is 0.8);
 - 1.2 the probability of a type I error " α " is allowed to be less than 5% (the probability of the erroneous acceptance of an alternative hypothesis is less than 0.05);
 - 1.3 the statistical criteria are 2-sided;
 - 1.4 the calculation of the sample size is based on the assumptions about the expected effects, mainly declared in the primary efficacy criterion of the Protocol;
 - 1.5 statistical null and alternative hypotheses are formulated as follows:

$$H_0: m_2-m_1 \le 0$$

$$H_1: m_2-m_1>0,$$

where $\mathbf{m_1}$ – mean disease duration in Ergoferon group,

m₂ – mean disease duration in Placebo group;

- 1.6 to assure potential adjustment of sample size or terminate the study due to inadequate efficacy/high efficacy, interim analysis will be carried out in which:
 - a. calculations will be made using O'Brien-Fleming boundary;
 - b. proportions of the subjects completing the study and yielding the results for interim and final analyses, will be taken as 0.5 and 1.0 (i.e. interim analysis will be made after recruitment of half of the planned number of the clinical study subjects.
- 1.7 therefore, sample size will be calculated taking into account
 - a. interim analysis;

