- 3. For the frequency analysis of 2×2 cross tables $-\chi^2$ -test (if the compared frequencies are greater than 5) or Fisher exact test (if one of the compared frequencies is less than 5).

CONFIDENTIAL Page 13 of 14

- 4. For the frequency analysis of cross tables with independent strata Cochran–Mantel–Haenszel test (modification of the χ^2 -test for multiple comparisons).
- 5. For the frequency analysis of data on the presence / absence of an event or outcome during repeated measures (cross tables with dependent strata) survival analysis.

To perform the above-mentioned non-parametric statistical analysis options, it is assumed that the following SAS procedures are used:

- FREQ Friedman test, χ^2 -test and / or Fisher exact test; Cochran–Mantel–Haenszel test.
- LIFETEST survival analysis.
- NPAR1WAY Mann-Whitney U-test.

Safety parameters

Adverse events recorded during the study will be grouped into frequency tables by severity, seriousness and relationship with the study drug.

Data presentation

Descriptive statistics will be provided for each study continuous / interval variable. Numerical data will be presented by mean, standard deviation, min and max values. Comparisons suggesting statistical conclusion will have the relevant confidence intervals. Outliers will be analyzed individually. The data will be grouped by visits. The categorical variables will be presented as frequency tables by visits.

CONFIDENTIAL Page 14 of 14

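### The plan does not say which day an early-discharge PCR sample belongs to, and under either reading the Day 6 negative rate in secondary endpoint 6 depends on recovery time

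*Combined protocol and SAP*

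**What the plan says.** Secondary endpoint 6 is defined by day: "Percentage of patients with negative PCR tests on Days 3, 4, 6, and 10 of observation versus baseline". The Study design section says that repeat stool PCR "will be performed on Days 3, 4, and 6 of inpatient observation and after discharge from the hospital (Day 10".

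The same section then makes an exception: "Patients who recovered while in hospital and are discharged from the unit earlier than at 5 days will undergo the procedures of Visit 6". Those procedures expressly include a sample taken for efficacy: "including the collection of biological specimens for PCR (efficacy evaluation". A note to the Schedule of study procedures also expects early leavers: "If the subject is discharged sooner than on day 6, the parent/adopter will be given a blister". Arrangements for stool after discharge appear only for the last visit: "All the subjects will receive sterile containers for stool storage and transportation on day 10", with a courier if that visit is by phone. Nothing similar is described for Day 6.

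Three statistical statements bear on the point.

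- Data presentation: "The data will be grouped by visits".
- The missing-data rule under Samples: "Mean value in Placebo group for the relevant day will be used to fill lacking/missing data".
- Non-parametric criteria, item 5, which lists survival analysis for outcomes recorded as present or absent at repeated assessments. It names neither endpoint 6 nor interval censoring.

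No section gives a window for Day 6 or says which day a discharge sample belongs to.

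**The concern.** Recovery triggers the early sample, and recovery is itself an efficacy outcome (secondary endpoints 2 and 3). The sampling time for the Day 6 result is therefore a post-randomisation variable that the drug is meant to change. If the arms recover at different speeds, their Day 6 rates mix different sampling times in different proportions. A child who leaves on Day 4 could supply practically the same specimen time for both Day 4 and Day 6. A child who leaves before Day 3 or Day 4 has no sample for that day.

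What is at stake is the reading of one secondary endpoint, the only one that measures the virus directly. A difference between arms at Day 6 could reflect when children went home, and a real difference in clearance could be diluted.

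**Working it through.** **Plan's own figure.** The documents give none for endpoint 6. The planned 143 per group serves here only as a yardstick for precision. It reproduces for the primary endpoint: 2 × 36² × (1.960 + 0.842)² / 12² = 141.3. An assumed O'Brien-Fleming inflation of about 1.008 brings this to 142.4, rounded up to 143.

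**How common early discharge could be.** Footnote 11 gives diarrhea durations of 1.9 ± 1.2 days (active) and 2.9 ± 1.8 days (placebo). Gamma and lognormal distributions with these means and SDs put the end of diarrhea within 4 days in about 94% of active and 77–80% of placebo children. With the planned 12-hour difference and 36-hour SD around 2.9 days, the shares are 86–88% and 80–82%. These are upper bounds on early discharge, because recovery also requires no vomiting, fever or dehydration (footnote 2) and not every recovered child leaves at once.

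**Reading A: the discharge sample counts as Day 6.** Let e be the share of an arm sampled early, and d the share of those children who are positive at discharge but would be negative by Day 6. The recorded rate is the true Day 6 rate minus e × d. The false difference (active minus placebo) is therefore −(e_A × d_A − e_P × d_P).

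Assumed inputs, none of them in the documents: the same exponential clearance in both arms, unrelated to recovery; median 5 days; all early leavers sampled on Day 4 (3 days after the start); Day 6 is 5 days after the start.

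- Negative at Day 6: 1 − 2^(−5/5) = 50.0%. Negative at Day 4: 1 − 2^(−3/5) = 34.0%. So d = 16.0% in both arms.
- 40% of active and 25% of placebo sampled early: 0.40 × 34.0 + 0.60 × 50.0 = 43.6%, against 0.25 × 34.0 + 0.75 × 50.0 = 46.0%. Difference −2.4 points.
- 50% and 20% sampled early: 42.0% against 46.8%. Difference −4.8 points.

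Varying the assumed clearance median:

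| Median (days) | Negative Day 6 | Negative Day 4 | d | 40% vs 25% early | 50% vs 20% early |
|---|---|---|---|---|---|
| 3 | 68.5% | 50.0% | 18.5% | −2.8 | −5.6 |
| 5 | 50.0% | 34.0% | 16.0% | −2.4 | −4.8 |
| 8 | 35.2% | 22.9% | 12.3% | −1.8 | −3.7 |

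If every early leaver is already negative at discharge and stays so, d = 0 and the bias is zero. If d differs between arms the sign can turn: with e = 40% and 25% and d_P = 16%, it does so once d_A falls below 0.25 × 16 / 0.40 = 10%.

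As an outer range, a simulation drew discharge times from the fitted gamma distributions, with 50–100% of eligible children leaving 0–1 day after diarrhea ended and clearance medians of 3 to 8 days. It gave −1.5 to −6.5 points under the 12-hour assumption and −2.4 to −11.1 under the footnote 11 durations. The extremes need every eligible child to leave as soon as diarrhea stops.

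**Yardstick.** At 143 per arm and rates near 45%, the standard error of a difference is √(2 × 0.45 × 0.55 / 143) = 5.9 points. The 2.4 and 4.8 points are therefore about 0.4 and 0.8 standard errors.

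**Reading B: the discharge sample is not used.** Day 6 is then missing because the child recovered. Let s_A and s_P be the negative rates among children still in hospital. Filling with the placebo mean leaves the placebo arm at s_P and gives the active arm (1 − e_A) × s_A + e_A × s_P. The difference becomes (1 − e_A) × (s_A − s_P). With 40% early leavers only 60% of the observed difference remains, and that difference comes only from children who recovered more slowly.

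**The case against.** The strongest reply is that no sentence files the discharge sample under Day 6. Endpoint 6, the sampling plan and the missing-data rule all speak of days. The sentence on grouping by visit stands among remarks on tables and descriptive statistics, and the document describes itself as a protocol summary. This stands: counting the sample as Day 6 is an inference, though a natural one for a Visit 6 procedure done for efficacy. It does not rescue the comparison, because the alternative is Reading B.

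The direction and size are also open to challenge. A reader might infer that the arms must show different Day 6 rates even with equal clearance, and that a true antiviral effect must be understated. The documents do not support that. It requires that the arms differ in recovery speed and that early leavers clear virus no sooner than other children. If the drug changes neither recovery nor clearance, discharge times match and no false difference arises. If clearance accompanies recovery, the bias shrinks towards zero. In the direction illustrated, the bias works against the faster-recovering arm, so it would not produce a false efficacy claim for that arm.

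Finally, a method close to the remedy is already listed: survival analysis for repeated presence/absence data. That is fair. The cover is partial, since it is not tied to endpoint 6 and interval censoring is not mentioned.

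**Conclusion.** The point holds as a gap in the plan. The discharge sample has no stated day, no true Day 6 stool is planned for early leavers, and both available readings make the Day 6 negative rate depend on recovery time. The arms are therefore not comparable at Day 6 if they recover at different speeds.

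The size cannot be known from the documents. If clearance is unrelated to recovery, it is about 2 to 5 points against the faster-recovering arm, under assumed clearance and discharge shares. That is less than one standard error at the planned size. The larger simulated values are limits, not estimates.

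The scope is small: one of seven secondary endpoints. Day 6 is the main problem, and Days 3 and 4 may also lose children who leave before them. Day 10 is scheduled for every child, and the primary endpoint is untouched.

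A reader might also conclude that restricting the Day 6 percentage to children sampled that day would solve it. It would not: the children left are mainly those who recovered slowly, which is again selection on a post-randomisation outcome.

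**What to change.** This is a cheap improvement, in the analysis plan only.

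- Record the actual date of every stool sample, including discharge samples.
- Make interval-censored time to first negative PCR the main between-arm comparison for endpoint 6. Each child contributes the interval from last positive to first negative, using all samples including discharge and Day 10. This refines the survival analysis already listed.
- Do not label discharge samples as Day 6, do not fill missing PCR results with the placebo mean, and do not test a Day 6 percentage restricted to children sampled that day.
- Report by-day percentages as descriptive, with Day 10 as the fixed-time comparison.
- Reconcile the two descriptions of early discharge: Study design uses a 5-day limit, the schedule note uses Day 6.

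The cost is slightly more analysis work, and the Day 6 percentage is no longer a formal comparison. One limit remains: the discharge sample is still triggered by recovery, so the interval-censored analysis assumes that its timing carries no further information on clearance. The Day 10 comparison does not need that assumption. If sampling can still be changed, a true Day 6 stool collected after discharge, using the Day 10 courier arrangement, would remove the Day 6 problem directly at extra logistical cost.

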³⁾ time to the absence of stools for ≥ 12 h which is not followed by new episodes of diarrhea (total stool frequency over 24 h – less than 3 times).

² Recovery criteria: absence of diarrhea, vomiting, symptoms of dehydration, and increased body temperature (based on daily examinations by pediatrician).

³ Worsening of illness: an increase in dehydration scores and worsening of non-specific symptoms, as evidenced by a decline in general appearance, increasing fatigue and drowsiness, refusal to eat and drink, severe tachycardia/bradycardia, unstable hemodynamics, tachypnea, hypo- or hyperventilation, circulation disorders, peripheral cyanosis, sunken eyes, severe dryness of skin and mucous/tongue, poor tissue turgor, absent tears, persistent vomiting, anuria/acute kidney injury, seizure/convulsions, and meningismus.

⁴ Hospital-acquired infection: a viral or bacterial infection (intestinal, respiratory or urinary tract infection, etc.) occurring after at least 48 h of hospital stay and confirmed by laborator tests.

Safety assessment

- Adverse events (AE) during the treatment, AEs severity and relations to the study drug, and AEs outcomes.
- Changes in vital signs and laboratory parameters (complete blood count test, biochemistry blood test and urinalysis).
- Percentage of patients with abnormal biochemistry.

Study design

Study design: an international multicenter, double-blind, placebo-controlled, randomized clinical trial in parallel groups.

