- 6. Availability of a patient information sheet (Informed Consent form) signed by the patient's parents/adopters to confirm the child's participation in the clinical trial signed by one parent/adopter of patient.

Exclusion criteria

1. Suspected bacterial intestinal infection.

CONFIDENTIAL Page 4 of 14

- 2. Suspected infectious diseases of another localization including pneumonia, meningitis, sepsis, otitis media, urinary tract infection, etc.
- 3. Severe intestinal infection⁷.
- 4. Severe dehydration (CDS score \geq 7).
- 5. Anuria (acute kidney injury).
- Medical history or prior diagnosis of serious diseases, including primary/secondary immunodeficieny, oncological disease, diabetes mellitus, infantile cerebral palsy, mucoviscidosis/cystic fibrosis etc.
- 7. Exacerbation or decompensation of a chronic disease, including diseases of the digestive system that would affect the patient's ability to participate in the clinical trial.
- 8. Malabsorption syndrome, including congenital or acquired lactose intolerance/lactase deficiency or any other disaccharidase deficiency and galactosemia.
- 9. Allergy/ intolerance to any of the components of study drugs.
- 10. Course administration of any medicines listed in the section "Prohibited concomitant treatment" for 2 weeks prior to the enrollment in the trial.
- 11. Participation in other clinical trials within 3 months prior to the enrollment in this study.
- 12. Patients whose parents/adopters, from investigator's point of view, will fail to comply with the observation requirements of the trial or with the dosing regimen of the study drugs.
- 13. The patient's parent/adoptive parent are a study specialist of the centre and is directly involved in the study, or is an immediate family member of the Investigator. Spouses, parents, children, or siblings, regardless of whether they are siblings or adopted are considered immediate family members.
- 14. The patient's parent/adoptive parent works for OOO "NPF "Materia Medica Holding", i.e. they are employees of the Company, temporary employees on a contract basis or appointed officials responsible for conduction of the study or their immediate family members.

Criteria for Withdrawal or Termination

- 1. The patient's inability or refusal of the patient or parents/adopters to follow the protocol requirements.
- 2. The necessity to use medications prohibited within this trial.
- 3. An adverse event requiring discontinuation of the study drug.

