- 4. The patient's or his/her parent/adopter wish to complete the study ahead of schedule for any reason.

CONFIDENTIAL Page 5 of 14

_

⁷ Criteria for a severe intestinal infection: sudden patient deterioration, sudden fatigue or even adynamia, marked apathy and drowsiness/excessive sleepiness and lethargy, dry mucous membranes, sunken eyes, loss of tearing, pool tissue turgor, lack of eye contact in the child on examination, aversion to food and drink, severe tachycardia/bradycardia, unstable hemodynamics, tachypnea, hypo- or hyperventilation, impaired microcirculation, peripheral cyanosis, slow capillary nail refill, persistent vomiting, anuria/acute renal disease, convulsions, and meningism.

- 5. Cases not specified by the protocol when, according to the investigator's opinion, further participation in the study harms the patient.
- 6. Incorrect inclusion of ineligible patient.
- 7. Early discharge of patient from hospital with persisting acute intestinal infection symptoms on days 2-5 of hospitalization, before the end of taking the study therapy at the parent's/adopter's request.

Number of subjects

It is planned to enroll 572 patients, which is expected to allow completion of all protocol procedures by at least 286 PCR-positive (for viral acute intestinal infection) patients (143 patients in the Ergoferon and Placebo groups).

Interim analysis

An interim statistical analysis will be performed as part of this study.

The interim analysis will be based on the patient assessment data and treatment outcomes recorded for the protocol-defined number of patients who have completed participation in the study.

Number of patients to be evaluated in the interim analysis:

144 patients (72 in the Ergoferon group and 72 in the Placebo group).

Number of patients to be evaluated in the final analysis:

286 patients (143 in the Ergoferon group and 143 in the Placebo group).

Treatment

Group 1

Name of the medicinal product: Ergoferon

Active ingredient: affinity purified antibodies to human gamma interferon -0.006 g*, affinity purified antibodies to histamine -0.006 g*, affinity purified antibodies to CD4 -0.006 g*

* Mixture of water-ethanol dilutions 100^{12} , 100^{30} , 100^{50} of active substance used for saturation of lactose monohydrate.

Excipients: Lactose monohydrate -0.267 g, microcrystalline cellulose -0.03 g, magnesium stearate -0.003 g.

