In case of special indications and/or complications, the pediatrician may prescribe syndrome-specific treatments, such as enteral (nasogastric) or pareteral (intravenous) rehydration salt formulations and detoxicants, antiemetics (Domperidone/Metoclopramide), antipyretics (Paracetamol/Ibuprofen, or Metamizole - for fever not relieved by paracetamol/ibuprofen).

Prohibited concomitant therapy

Two weeks prior to enrollment⁹ and during the study (from the time of signing the information sheet (Informed Consent Form) and screening initiation), it is prohibited to administer the following medications:

- 1. Antibacterials, including enteric antimicrobial agents (sulfonamide and trimethoprim preparations).
- 2. Antidiarrheal microorganisms (excluding Linex®).
- 3. Intestinal antiinflammatory agents.
- 4. Intestinal adsorbents (excluding diosmectite).
- 5. Antispasmodics and antipropulsives.
- 6. Antiemetics (excluding domperidone and metoclopramide).
- 7. Laxatives.
- 8. Digestives, including enzymes.
- 9. Prebiotics.
- 10. Nonsteroidal antiinflammatory drugs (excluding ibuprofen).
- 11. Analgesics and antipyretics (excluding paracetamol and metamizole).
- 12. Antiviral drugs except for Ergofern and Oseltamivir (Tamiflu®), which are prescribed within this study.
- 13. Immunostimulants, including interferon inducers (acridone acetic acid, meglumine acridone acetate, polyadenylic acid + polyuridylic acid, methylphenylthyomethyl-dimethylaminomethyl-hydroxybromindol carboxylic acid ethyl ether, sodium oxo-dihydro-acridinyl acetate, cagocel, tilorone, umifenovir); pidotimod, synthetic immunostimulants (levamizol or alfa-glutamyl-tryptophan); bacterial immunomodulators (including ribomunyl, ribonucleate sodium, deoxyribonucleate sodium, IRS 19, umudon etc.);
- 14. Immune sera and immunoglobulins (J06).
- 15. Vaccines.
- 16. Antineoplastic agents and antineoplastic endocrine therapy.
- 17. Immunosuppressants.
- 18. Corticosteroids for systemic use.

[figure not shown]
CONFIDENTIAL Page 8 of 14

_

⁹ A single use by a patient of any of the drugs on the 'non-permitted medications' list (sections 1-11) in the course of 48 hours prior to enrollment is not considered a non-inclusion criterion.

- 19. Homeopathic medicines.
- 20. Drugs known to previously cause allergic reactions in the patient.

Study design scheme

Schedule of study procedures

Procedure/Day	Day 1	Day 2	Day 3	Day 4	Day 5	Day 6	Day 10±1
Informed consent	+						
Collection of complaints	+	+	+	+	+	+	

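### Children withdrawn because of an endpoint 7 event have no planned follow-up: endpoint 7 is undercounted in the Per Protocol set and at the interim, and their later outcomes are filled with a placebo mean in the Full Analysis Set

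*Combined protocol and SAP*

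**What the plan says.** Secondary endpoint 7 is "Percentage of patients with worsening of illness³ and/or hospital-acquired infection⁴". Footnote 4 defines the second component as "a viral or bacterial infection (intestinal, respiratory or urinary tract infection, etc.) occurring after at least 48 h of hospital stay", with laboratory confirmation.

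Under Prohibited concomitant therapy, item 1 is "Antibacterials, including enteric antimicrobial agents", and the ban runs throughout the study. Under Criteria for Withdrawal or Termination, three items bear on a child who does badly:

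- item 2: "The necessity to use medications prohibited within this trial"
- item 3: "An adverse event requiring discontinuation of the study drug"
- item 5: "Cases not specified by the protocol when, according to the investigator's opinion, further participation in the study harms the patient"

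The Samples section limits the Per Protocol set to children who finish therapy with no missed visit and no significant deviation. The Full Analysis Set, used for the ITT analysis, leaves out randomized children for four reasons only: ineligibility, no dose taken, no data after randomization, and early discharge with persisting symptoms at the parent's request. Missing data are to be filled with the placebo-group mean for the relevant day. The interim analysis uses patients who have completed participation.

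**The concern.** Endpoint 7 measures a bad course, and one form of bad course also ends the child's participation. Criterion 3 makes a stop of study drug a ground for withdrawal, so the plan treats withdrawal as more than stopping tablets. No section says that the diary, CDS, stool PCR or Visit 7 go on afterwards. By contrast, children who recover and go home early are expressly given the Visit 6 procedures, including PCR and safety tests. Data collection is thus written down for an early good outcome and not for a bad one.

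Removal then depends on something that happens after randomization and that treatment could influence. In a completers-only set the two arms are no longer the groups that randomization made. The interim analysis can stop the trial or change its size, so the same selection could feed that decision.

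**Working it through.** **The plan's own figure.** Inputs from Evaluation of sample size: difference 12 h, SD 36 h, two-sided 5%, power 80%, O'Brien-Fleming looks at 0.5 and 1.0.

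- Fixed design: 2 × 36² × (1.960 + 0.842)² / 12² = 141.3 per group.
- Two-look inflation factor 1.0078: 142.4, so 143 at the final analysis. Half is 71.2, so 72 at the interim.
- Enrollment: 286 / (1 − 0.5) = 572.

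The stated 72, 143, 286 and 572 reproduce. They are sized for diarrhea duration in Per Protocol completers, not for endpoint 7.

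**One child followed through the plan.** A laboratory-confirmed bacterial infection appears on Day 4, after more than 48 h in hospital, and needs an antibacterial.

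1. Endpoint 7: this is an event under footnote 4.
2. Withdrawal: criterion 2 is met.
3. Per Protocol set: the child did not complete as planned and is out.
4. Interim analysis: the child did not complete participation and is out.
5. Full Analysis Set: criteria 2, 3 and 5 are not among its four exclusions, so the child stays. The infection precedes the withdrawal, so the event can be counted if it was recorded.
6. Later outcomes in the Full Analysis Set: diarrhea and illness duration (if not yet ended) and the later PCR results are missing. A placebo-group daily mean gives this child an average course. The rule is worded for daily values, and how it applies to a duration is not stated. For a yes/no endpoint a mean is not a possible individual value.

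**Size in the Per Protocol set.** The documents give no event rate, so p (true rate) and f (share of event children withdrawn) are assumptions. The observed rate is p(1 − f) / (1 − pf).

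- p = 3%, f = 2/3: 0.01 / 0.98 = 1.0%.
- p = 6%, f = 2/3: 0.02 / 0.96 = 2.1%.
- From 143 children per arm before removal: 143 × 3% = 4.3 and 143 × 6% = 8.6 events. One third is kept, leaving 1.4 and 2.9.

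A wider range for the observed rate:

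| True p | f = 25% | f = 50% | f = 75% | f = 100% |
|---|---|---|---|---|
| 5% | 3.8% | 2.6% | 1.3% | 0% |
| 10% | 7.7% | 5.3% | 2.7% | 0% |
| 20% | 15.8% | 11.1% | 5.9% | 0% |

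For assumed true rates of 10% and 20%, with 143 per arm before removal, the power of a two-sided 5% comparison of proportions is 66% at f = 0, 41% at f = 50% and 24% at f = 75%.

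Equal f in both arms shrinks the difference but leaves the ratio near 2 (2.1% / 1.0%). Unequal f can remove the contrast. With p = 3% and f = 50% the observed rate is 0.015 / 0.985 = 1.5%. With p = 6% and f = 75% it is 0.015 / 0.955 = 1.6%.

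In the Full Analysis Set, f is about 0 for endpoint 7 if the event is recorded by the time of withdrawal. The loss there is in what comes after.

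**The case against.** The case on the other side has real force.

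- **A reader might infer that endpoint 7 is lost altogether.** The documents do not support this. Withdrawals under criteria 2, 3 and 5 stay in the Full Analysis Set, and the event comes before the withdrawal.
- **A reader might infer that worsening children are withdrawn as such.** They are not. Nasogastric or intravenous rehydration, antiemetics and antipyretics are allowed for complications. Criterion 3 needs an adverse event that stops the drug, and criterion 5 needs a judgement of harm. Some deteriorating children may leave this way, but only the bacterial route is firm. A viral hospital-acquired infection does not in itself call for an antibacterial.
- **A reader might infer that footnote 6 deletes later bacterial infections.** It states "The data of a patient whose PCR test indicates a bacterial etiology of acute intestinal infection will not be included in the analysis" and names no specimen, and bacteria are tested again on Days 3, 4, 6 and 10. But its marker sits on the pre-treatment assay that diagnoses the presenting illness, and the repeat-PCR text does not carry it. Only a strained reading extends it to an organism acquired later.
- **The loss of CDS data is small.** CDS is an endpoint only at 24, 48 and 72 h, so a Day 4 event costs little or none of it. The Safety population keeps every treated child.
- **A Per Protocol set omits non-completers by design,** and endpoint 7 is the last of seven secondary endpoints.
- **The document is a protocol summary.** A full protocol might describe follow-up after withdrawal.

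All of this narrows the point. What stands is that no post-withdrawal follow-up is stated, that the sample size and the interim analysis rest on completers, and that the only missing-data rule suits neither a deteriorating child nor a binary endpoint.

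**Conclusion.** The point holds in this limited form. A bacterial hospital-acquired infection that needs an antibacterial is both an endpoint 7 event and a ground for withdrawal. As written, the plan collects nothing further from that child. Endpoint 7 is undercounted in the Per Protocol set and the interim analysis. In the Full Analysis Set the event can be counted, but later outcomes are missing and are replaced by a placebo average.

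The size is unknown. The illustration of 3% and 6% showing as about 1.0% and 2.1% rests on assumed rates and an assumed two-thirds withdrawal share. The direction of bias in the arm comparison cannot be fixed from the documents, because it depends on how f differs between arms. The conclusion also assumes that no fuller document sets out follow-up after withdrawal. It is worth correcting because the correction is cheap.

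**What to change.** 1. Separate stopping study tablets from leaving the study. For children who meet criteria 2, 3 or 5, continue the already scheduled diary, CDS, PCR and Visit 7 unless the parent withdraws consent. This changes neither when treatment is stopped nor which drugs are allowed.
2. Make the Full Analysis Set, restricted by baseline PCR, the main set for endpoint 7. Score a withdrawal caused by worsening or hospital-acquired infection as an event. Do not use placebo-mean filling for these children.
3. As a clarification only, state that footnote 6 refers to the pre-treatment specimen.

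The cost is protocol and SAP wording, and follow-up uses visits already planned. One downside is that outcomes recorded after a prohibited drug also reflect that drug, so add a sensitivity analysis that ends at its start. The Full Analysis Set would still leave out children discharged early with persisting symptoms (criterion 7 and the fourth exclusion). That is a separate route, which this change does not close.
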